6.4 Other Safety Parameters/ Clinical Assessments

The following information will be analyzed descriptively and corresponding details on the subject level will be provided in data listings.

6.4.1 Data Points

- ECOG status •
- Vital signs •
 - 0 blood pressure
 - heart rate 0
 - body temperature 0
 - 0 body weight

The following information will only be provided in data listings:

- Pregnancy test (if applicable) •
- Physical examination •
- Quality of life •
- ECG •
- Chest X-Ray •
- Subsequent cancer therapy •

Adapted from: Page 17 of 23 STAT03_A Statistical Analysis Plan Version 6.0, Effective Date 16-Feb-2018 Confidential and intellectual property of Assign DMB. No part of this document or its contents may be duplicated, referenced, published or otherwise disclosed in any form or by any means without prior written consent of Assign DMB.

7. LIST OF TABLES, DATA LISTINGS AND FIGURES

Numbering of tables, listings and figures will follow principles as below:

• Tables and figures numbering will begin with number 14, listings with number 16.2.

Numbering of Tables (digits after tables/figures prefix):

- First digit will indicate information type shown (1= overall, 2= baseline, 3= efficacy, 4= safety)
- Second digit will represent table/listing/figure type.

7.1 List of Tables

7.1.1 Overall Study Information

| No | Legend | Content |
|--------|----------------------------------|---|
| 14.1.1 | Patient overview (All patients) | Eligible patients Study Populations (ITT, PP, Safety) Screening completion / screening failures incl. reason End of study incl. reason for study end |
| 14.1.2 | Attended visits (ITT Population) | |

7.1.2 Baseline Evaluation

| No | Legend | Content |
|----------|---|---|
| 14.2.1 | Demographics and baseline characteristics | Age at informed consent |
| | (ITT Population) | Gender |
| | | Race |
| | | Body weight and height |
| | | Smoking status |
| 14.2.2 | Disease history (ITT Population) | Cancer history |
| | | Histological type |
| | | Previous cancer treatment (any) |
| 14.2.3 | Medical history by System Organ Class and | |
| | Preferred Term (ITT Population) | |
| 14.2.4-6 | Tables 14.2.1-3 will be repeated for the PP | |
| | Population. | |

7.1.3 Efficacy Analysis

| No | Legend | Content |
|--------|--------------------------------------|----------------------------------|
| 14.3.1 | Tumor Response at Pre-Surgery Visit | Overall response |
| | (PP Population) | Δ tumor size |
| 14.3.2 | Tumor Regression Grading Stage (PP | |
| | Population) | |
| 14.3.3 | Kaplan-Meier Statistics for Disease- | |
| | Free Survival (PP Population) | |
| 14.3.4 | Kaplan-Meier Statistics for Overall | |
| | Survival (PP Population) | |
| 14.3.5 | Tumor Staging (PP Population) | Tumor stage |
| 14.3.6 | Tumor Marker Values Over Time (PP | CEA |
| | Population) | Cyfra 21-1 |
| 14.3.7 | Tumor Marker Value's Change from | CEA |
| | Baseline (PP Population) | Cyfra 21-1 |

Confidential and intellectual property of Assign DMB. No part of this document or its contents may be duplicated, referenced, published or otherwise disclosed in any form or by any means without prior written consent of Assign DMB.

Page 19 of 23

| 14.3.8 | Lung function test results (PP | VC MAX |
|-----------|--|---------------|
| | Population) | FVC |
| | | VC IN |
| | | • FEV1 |
| | | FEV 1% VC MAX |
| | | DLCO SB |
| | | DLCO/VA |
| | | DLCOc SB |
| | | DLCOc/VA |
| | | • pC02 |
| | | • pO2 |
| 14.3.9-16 | Tables 14.3.1-8 will be repeated for the ITT Population. | |

7.1.4 Safety Analysis

| No | Legend | Content | | | |
|----------------|--|---|--|--|--|
| Adverse Events | | | | | |
| 14.4.1 | Adverse Events Overview (Safety Population) | Any AE Any AE of clinical interest Any related AE Any severe AE Any AE grade 2-4 Any related severe AE Any related AE grade 2-4 Any related AE grade 2-4 Any SAE Any related SAE Any AE requiring treatment discontinuation Any AE requiring treatment dose modification | | | |
| 14.4.2 | Adverse Events by Maximum Severity (Safety Population) | Any AE Any related AE | | | |
| 14.4.3 | Adverse Event by Highest Relationship (Safety Population) | Any AE Any AE grade 2-4 Any SAE | | | |
| 14.4.4 | Adverse Events by SOC and Preferred Term (Safety Population) | Any AE Any AE grade 2-4 Any related AE Any related AE grade 2-4 Any SAE Any related SAE Any AE requiring study treatment discontinuation | | | |
| Laborato | bry Parameters | | | | |
| 14.4.5 | Hematology Values over Time (Safety Population) | - | | | |
| 14.4.6 | Hematology Value's Change from Baseline (Safety Population) | | | | |
| 14.4.7 | Hematology Values above and below Normal Range by Time Point (Safety Population) | | | | |
| 14.4.8 | Clinical Chemistry and Coagulation Values over Time (Safety Population) | | | | |
| 14.4.9 | Clinical Chemistry and Coagulation Value's Change from Baseline (Safety Population) | | | | |

Adapted from: STAT03_A Statistical Analysis Plan

Version 6.0, Effective Date 16-Feb-2018

Confidential and intellectual property of Assign DMB. No part of this document or its contents may be duplicated, referenced, published or otherwise disclosed in any form or by any means without prior written consent of Assign DMB.

| 14.4.10 | Clinical Chemistry and Coagulation Values above and below Normal Range by Time Point (Safety Population) | | |
|----------|--|---|------------------|
| Other Sa | fety Parameters | | |
| 14.4.11 | ECOG Status (Safety Population) | | |
| 14.4.12 | Vital Signs (Safety Population) | ٠ | Blood pressure |
| | | • | Heart rate |
| | | • | Body temperature |
| | | • | Body weight |

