2.4 Primary endpoint

- frequency and severity of adverse events including peri- and post-operative complications (grade 2-4 AEs according to NCI-CTCAE V4.03)
 - number of patients treated in compliance with protocol
- tumor response evaluation

clinical response parameters:

- o response rates (∆ tumor size / lymph node size), according to RECIST
 1.1 criteria
- $\circ \Delta$ PET-activity (standardized uptake value [SUV])

Pathologic response parameters:

• Pathologic regression grading according to Junker criteria [12]

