8.4.4 Safety evaluation

Adverse events:

All information recorded such as onset date, stop date, duration, maximum intensity, seriousness, relationship to study drug and outcome will be listed.

Summary tables will be presented. These tables provide the number and percentage of patients with adverse events. Associated adverse event tables present the total number of patients reporting at least one specific event and the maximum toxicity grade. Thus, patients reporting more than one episode of the same event are counted only once by the worst grade per patient.

Tabulations consist of the number and percentages of patients involved per CTC category and CTC term, the highest relation to study drug, and the maximum severity. Special tables will be displayed for CTC grade III / IV adverse events and for adverse events resulting in discontinuation of the trial. Additionally, analysis will be restricted to adverse events judged to be at least possibly related to study drug.

Laboratory parameters:

Abnormal laboratory parameters will be tabulated according to incidence and severity according to NCI CTCAE V4.03 and analyzed descriptively.

9 Independent Data Monitoring Committee

An Independent Data Monitoring Committee (IDMC) has been convened to assess the safety data, and provide recommendations to the Sponsor and Coordinating Investigator upon the stop or continuation of the study. The members of the IDMC serve in their individual capacity and provide their expertise and recommendations. The IDMC will review cumulative study data to evaluate subject safety, conduct an interim analysis and reassess the risk/benefit of the study.

The role and responsibilities of the IDMC are described in detail in a separate IDMC Charter.

10 Data Quality Assurance

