1.3 Endpoints

- 1.3.1 Primary Endpoint
 - Frequency and severity of AEs including peri- and post-operative complications (grade 2-4 AEs according to NCI-CTCAE V4.03)
 - o number of patients treated in compliance with protocol
 - Tumor response evaluation

clinical response parameters:

- o response rates (Δ tumor size / lymph node size), according to RECIST 1.1 criteria
- Δ PET-activity (standardized uptake value [SUV]) (analysis of this end point is not covered in this SAP)
 Pathologic response parameters:
- Pathologic regression grading according to Junker criteria (see Appendix 3 of CSP)
- 1.3.2 Secondary Endpoints
 - disease free survival
 - overall survival

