6.2.1 Data Points

- Adverse Event Overview
 - o Any AE
 - Any AE of clinical interest
 - o Any related AE
 - o Any severe AE
 - Any AE grade 2-4
 - Any related severe AE
 - o Any related AE grade 2-4
 - o Any SAE
 - Any related SAE
 - Any AE requiring study treatment dose modification
 - o Any AE requiring study treatment discontinuation
- Adverse Events by maximum severity
 - o Any AE
 - o Any related AE
- Adverse Event by highest relationship
 - o Any AE
 - o Any AE grade 2-4

Adapted from:

STAT03_A Statistical Analysis Plan Version 6.0, Effective Date 16-Feb-2018

Confidential and intellectual property of Assign DMB. No part of this document or its contents may be duplicated, referenced, published or otherwise disclosed in any form or by any means without prior written consent of Assign DMB.

- o Any SAE
- Adverse Events by SOC and preferred term
 - o Any AE
 - Any related AE
 - Any AE grade 2-4
 - o Any related AE grade 2-4
 - Any SAE
 - Any related SAE
 - Any AE requiring study treatment discontinuation
- 6.2.2 Definition
 - Severe AE: AEs with severities of Grade 3-5 (severe or medically significant, severe or life threatening, death) will be considered as severe AEs
 - Missing causality assessment for adverse events will lead to handling of the AE as "related", see Section 7.3 of the CSP.

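### The SAP states no AE table by preferred term that separates grade 3 or higher, although protocol 8.4.4 commits to grade III/IV tables and to the worst grade for each specific event

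*SAP*

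**What the plan says.** The first primary endpoint in protocol 2.4 is "frequency and severity of adverse events including peri- and post-operative complications". SAP 1.3 repeats it with the same bracket: "Frequency and severity of AEs including peri- and post-operative complications (grade 2-4 AEs according to NCI-CTCAE V4.03").

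Protocol 8.4.4 describes how AEs are to be reported:
- "Associated adverse event tables present the total number of patients reporting at least one specific event and the maximum toxicity grade". A patient with several episodes of one event counts once, at the worst grade.
- Tabulation covers "patients involved per CTC category and CTC term, the highest relation to study drug, and the maximum severity".
- High-grade events get an output of their own: "Special tables will be displayed for CTC grade III / IV adverse events". The same sentence promises tables for AEs that led to discontinuation.

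The SAP defines a severe AE as grade 3-5 (6.2.2) and plans these outputs (6.2.1, 7.1.4, 7.2.4):
- Table 14.4.1, the overview, counts patients with a severe AE and patients with a related severe AE.
- Table 14.4.2 gives maximum severity for all AEs and for related AEs.
- Table 14.4.4, "Adverse Events by SOC and Preferred Term (Safety Population"), has seven blocks: all AEs, grade 2-4, related, related grade 2-4, SAEs, related SAEs, and AEs requiring discontinuation of study treatment.
- Listings 16.2.4.3 and 16.2.4.7 show severe and related severe AEs patient by patient, with preferred term and CTCAE grade.

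SAP 6.2.3 attaches 95% Wilson intervals to the AE summary tables. SAP 2.14 lists two changes from the protocol, screening-failure data in listings and omitted statistical tests. Neither concerns the AE tables.

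**The concern.** Severity is half of the primary safety endpoint, and the protocol says that it will be shown for specific events. The SAP carries the discontinuation part of the 8.4.4 sentence into its by-term table but not the grade III/IV part. From the tables as stated, a reader learns how many patients had some severe AE, but not which toxicities were severe or how often each was. No severe-toxicity rate for a named event receives an interval.

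The boundary that is pooled over is one the protocol itself uses. Its Table 1 treats grade 2 and grade 3-4 differently for pneumonitis, for nephritis or renal failure, and for raised liver values.

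**Working it through.** The plan gives no figure to reproduce on this point. The check compares protocol commitments with SAP outputs.

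| Protocol 8.4.4 commitment | SAP output | Met? |
|---|---|---|
| Patients per specific event with maximum grade | 14.4.4 is by term without a grade breakdown; 14.4.2 gives maximum severity with no by-term layout stated | Not as stated |
| CTC category and term; highest relation; maximum severity | 14.4.4, 14.4.3 and 14.4.2 respectively | Yes as three separate tabulations; not as a cross-tabulation |
| Special tables for grade III/IV AEs | Two overall counts of grade 3-5 in 14.4.1; patient listings | No dedicated table |
| Tables for AEs leading to discontinuation | Block in 14.4.4 | Yes |

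**What the pooled cut hides (illustration).** The event count is assumed: suppose 3 of 30 patients have grade 2-4 pneumonitis, and all 30 are in the Safety population.

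The Wilson interval for x of n, with p = x/n and z = 1.96, is

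(p + z²/2n ± z√(p(1−p)/n + z²/4n²)) / (1 + z²/n).

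Here p = 0.1, z²/n = 0.12805, z²/2n = 0.06403 and z²/4n² = 0.001067.
- Centre: (0.1 + 0.06403)/1.12805 = 0.1454.
- Half-width: 1.96 × √(0.003 + 0.001067)/1.12805 = 0.1108.
- Interval: 3.5% to 25.6%.

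The grade 2-4 line therefore reads 10% (3.5% to 25.6%). The number of ways to divide three patients among grades 2, 3 and 4 is C(3+2, 2) = 10, and every one of them gives this same line. The number at grade 3-4 may be anything from 0 to 3. A severe block would show 0/30 (Wilson 0% to 11.4%) at one end and 3/30 (3.5% to 25.6%) at the other. With six patients, C(6+2, 2) = 28 splits fit and the grade 3-4 count may be 0 to 6.

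**What the other blocks of 14.4.4 add.** The SAE block recovers part of the lost information, because a life-threatening event is serious by protocol 7.2.2. Seriousness and grade are nevertheless different criteria. Any event that prolongs a hospital stay is serious whatever its grade, which matters for post-operative complications, and a grade 3 event need not be serious. The discontinuation block can respond only while a dose is still due. There are two doses and surgery follows them, so it cannot grade post-operative events. Comparing all AEs with grade 2-4 by term isolates events outside grades 2-4, but does not separate grade 2 from grade 3 or 4. A fatal event lies outside the grade 2-4 blocks, and no by-term block identifies it as fatal.

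**The case against.** The case for leaving the SAP as it is has several parts.

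- **Severity is tabulated.** Table 14.4.1 has two severe-AE counts, Table 14.4.2 gives maximum severity, and Wilson intervals are planned. This stands. A reader might infer that the severity part of the endpoint goes unreported, and the documents do not support that. The gap is by specific event.
- **Table 14.4.2 might be by term.** No table shells are given, and its labels are the same as those used as event filters in 14.4.4. This also stands, so the fair statement is that a by-term layout is not specified. Against it, the SAP names SOC and preferred term only for the separate AE table 14.4.4.
- **Two of the protocol sentences are weaker than they look.** The sentence beginning "Tabulations consist of the number and percentages of patients involved per CTC category and CTC term" can be read as three separate tabulations, and the grade III/IV sentence does not say that its tables are by term. Both readings are fair. The sentence on specific events with maximum grade does not depend on them, and two overall counts are hardly the special tables promised.
- **Pooling grades 2-4 follows the endpoint's own bracket.** Correct. Those rows are legitimate; the finer breakdown is what is missing.
- **Mild and life-threatening cases would not look identical.** A reader might infer that three grade 2 and three grade 4 pneumonitis cases give the same Table 14.4.4. Only the grade 2-4 line would be the same. The SAE block, and possibly the discontinuation block, would be expected to differ.
- **With 30 patients the listings suffice.** They do keep term and grade, so severe events can be counted by hand. They give no counts, percentages or intervals, and the protocol promised tables.

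**Conclusion.** The point holds as a gap in table specification. The SAP's stated table list omits an output that protocol 8.4.4 promises for the severity part of the primary safety endpoint, and SAP 2.14 does not declare the omission. The only stated by-term grade cut is pooled 2-4. In the assumed example of three affected patients, it leaves the grade 3-4 count anywhere from 0 to 3.

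The size is modest. The data are collected and listed and no estimate is biased. The early stopping rule (protocol 5.4) and the feasibility criterion (protocol 8.1) both concern resection, so neither is affected. The conclusion rests on reading Table 14.4.2 as the SAP describes it, without a by-term breakdown. If one is intended, a sentence saying so would supply maximum grade by term, and the severe blocks in 14.4.4 would then be the remaining addition.

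**What to change.** 1. Add two blocks to Table 14.4.4, in SAP 6.2.1 and 7.1.4: severe AEs (grade 3-5) and related severe AEs, with the Wilson intervals already planned.
2. State that Table 14.4.2 is produced by SOC and preferred term, with each patient counted once per term at the maximum CTCAE grade. Grade III/IV can then be read separately from grade 5, as the protocol's wording requires.
3. If either output is not wanted, declare the departure from protocol 8.4.4 in SAP 2.14 with a reason.

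The cost is a few extra table blocks. Grade, causality and preferred term are already in the AE listings, and the severe flags already serve Table 14.4.1 and Listings 16.2.4.3 and 16.2.4.7. No new data are needed.

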7.2 List of Data Listings

7.2.1 Overall Study Information

| No | Legend | Content |
|----------|---|---|
| 16.2.1.1 | Patient Overview (All patients) | Patient ID, Date of written informed consent, |
| | | Version of informed consent, Version of informed |
| | | consent form, Patient eligible, Reason not |
| | | eligible, Planned date of treatment start, ITI |
| | | population, PP population, Safety population |
| 16.2.1.2 | Attended visits (ITT Population) | Patient ID, Visit, Planned date of visit, Actual |
| | | date of visit, Days between planned and actual |
| | | date, Reason outside time window, Days |
| | | between Visit 1 and Discharge |
| 16.2.1.3 | End of study details (ITT Population) | Patient ID, Date of study end, Date of last |
| | | contact when patient was alive, Reason for study |
| | | end, Specification lost to FU/other reason, Death |
| | | date, Primary cause of death, Date of pregnancy |
| | | noticed, Pregnancy status |
| 16.2.1.4 | Violated Inclusion/ Exclusion Criteria (ITT | Patient ID, Criterion category, Criterion, Answer |
| | Population) | |
| 16.2.1.5 | Protocol violations (All patients) | Patient ID, Protocol deviation category, Protocol |
| | | deviation description, Classification, Reason for |
| | | classification |

7.2.2 Baseline Data

| No | Legend | Content |
|----------|---|---|
| 16.2.2.1 | Demographics and baseline characteristics (ITT Population) | Patient ID, Gender, Year of birth, Age at informed consent, Body height, Body weight, Race, Childbearing potential, Reason no childbearing potential, Smoking status, Prev. smoker duration abstinence [years], Total tobacco consumption [pack years] |
| 16.2.2.2 | Cancer history (ITT Population) | Patient ID, Any cancer history within 5 years prior to screening, Specification, Any treatments of previous cancer, Number of previous cancer treatments |
| 16.2.2.3 | Previous cancer treatment details (ITT Population) | Patient ID, Type of prior treatment, Start date of prior treatment, Stop date of prior treatment, Location/ description |
| 16.2.2.4 | Tumor diagnosis (ITT Population) | Patient ID, Date of first NSCLC diagnosis, NSCLC location, Histologically/ cytologically confirmed NSCLC, Date of initial biopsy, Date of confirmation, Method, Histological type |

Adapted from: STAT03_A Statistical Analysis Plan Version 6.0, Effective Date 16-Feb-2018 Page 20 of 23

Confidential and intellectual property of Assign DMB. No part of this document or its contents may be duplicated, referenced, published or otherwise disclosed in any form or by any means without prior written consent of Assign DMB.

| 16.2.2.5 | Imaging date and time at screening (ITT | Patient ID, PET/CT performed, Date of PET/CT, |
|----------|---|--|
| | Population) | MRI brain performed, Date of MRI brain |
| 16.2.2.6 | Medical History (ITT Population) | Patient ID, MH number, Condition, Start date, End |
| | | date/ ongoing, Treated with medications at |
| | | screening, Start date unknown - prior to IC, End |
| | | date unknown - prior to IC |
| 16.2.2.7 | Prior/ Concomitant Medications (ITT Population) | Patient ID, CM number, Medication (trade name |
| | | preferred), Start Date, Start date unknown but |
| | | prior IC, End Date/ ongoing, Single-dose and unit, |
| | | Frequency, Route of Administration, Indication |
| 16.2.2.8 | Prior/ Concomitant Procedures (ITT Population) | Patient ID, CP number, Procedure, Start Date, |
| | | Start date unknown but prior IC, End Date/ |
| | | ongoing, End Date unknown but prior IC, |
| | | Indication |

7.2.3 Efficacy Data

| No | Legend | Content |
|----------|---|---|
| 16.2.3.1 | Screening Tumor Assessment (ITT Population) | Patient ID, Visit, Date of assessment, Number of |
| | | target lesions, Current sum LD [mm], Current |
| | | sum LD present, Number of non-target lesions, |
| 16.2.3.2 | Tumor Response at Pre-Surgery Visit (ITT | Patient ID, date of assessment, Any new |
| | Population) | lesions, New lesion location, New lesion |
| | | present, Date of progression, Current sum LD |
| | | [mm], current sum LD present, Baseline sum |
| | | LD [IIIII], A lumor size, Target lesion response |
| | | Reason inconsistent (TL response) Non-target |
| | | lesion response. Non-target lesion response |
| | | present. Overall response calculated. Overall |
| | | response investigator. Reason inconsistent (OA |
| | | response) |
| 16.2.3.3 | Target Lesion Details (ITT Population) | Patient ID, Visit, Target lesion, Location, |
| | | Description of location, Method, Diameter [mm], |
| | | Lesion present, Lesion too small to measure, |
| | | Lesion diameter (calculated) [mm] |
| 16.2.3.4 | Non-Target Lesion Details (ITT Population) | Patient ID, Visit, Non-Target lesion(s), Location, |
| | | Number of lesion(s), Description of location, |
| | | Method, Lesion(s) still present, Lesion(s) not |
| 16235 | Histology (ITT Population) | ASSESSED Patient ID. Tumor regression grading performed |
| 10.2.3.3 | | Date tumor regression grading Regression |
| | | grading stage Reason regression grading not |
| | | performed. Tumor size (largest diameter) [mm]. |
| | | Histologic subtype, Adenocarcinoma subtype |
| 16.2.3.6 | Overall Response (ITT Population) | Patient ID, OS [months], OS censored, DFS |
| | | [months], DFS censored |
| 16.2.3.7 | Tumor Staging (ITT Population) | Patient ID, Visit, Stage identifier, Stage |
| 16.2.3.8 | Tumor Markers (ITT Population) | Patient ID, Visit, Has blood sample been drawn, |
| | | Date of sample drawn, Actual age [years], |
| | | Parameter, Value, Unit, Clinically relevant, |
| 40.0.0.0 | Lung Function (ITT Deputching) | Causal relationship |
| 10.2.3.9 | Lung Function (III Population) | Patient ID, VISIT, Lung Tunction test, Test |
| | | Parameter (Rest) Value Unit ((Rest) value) |
| | | Rest/target value [%] |
| 16.2.3.9 | Lung Function (ITT Population) | Causal relationship Patient ID, Visit, Lung function test, Test performed, Date test performed, Method, Parameter, (Best) Value, Unit ((Best) value), Best/target value [%] |

Page 21 of 23

| 16.2.3.10 | Translational research (ITT Population) | Patient ID, Visit, Blood sample for biomarkers |
|-----------|---|--|
| | | drawn, Date of blood sample drawn |
| 16.2.3.11 | Survival status/ Follow-up (ITT Population) | Patient ID, Visit, Patient alive, Tumor |
| | | recurrence, Date of diagnosis, CT thorax scan |
| | | performed, X-ray performed |

